## **4.2.2 Safety laboratory data**

Measurements below the limit of quantification (BLQ) will be imputed with half of the lower limit of quantification (LLOQ) for the purpose of calculating change from PS0016 Baseline and for descriptive statistics. Measurements above the limit of quantification (ALQ), if applicable, will be imputed to the upper quantification limit.

These rules will be applied to all numeric safety laboratory data including clinical chemistry, hematology and urinalysis variables.

### **4.2.3 Bimekizumab concentration data**

Measurements that are BLQ will be imputed with LLOQ/2 for the purpose of calculating the geometric mean and its 95% CI, the geoCV, the arithmetic mean, and SD for summaries and figures.

For the individual figures, any concentrations that are BLQ will be imputed with LLOQ/2.

Additional rules for PK data summaries are provided in [Section 9](#).

### **4.2.4 Dates and times**

Partial dates may be imputed for the following reasons:

- Classification of AEs as treatment-emergent

- Classification of medications as prior or concomitant

Imputed dates will not be shown in the listings; all dates will be displayed as reported in the database.

The following rules will be applied for partial start dates with respect to the first dosing in PS0018:

- If only the month and year are specified and the month and year of first dosing is not the same as the month and year of the start date then use the 1st of the month. If time is missing this will be imputed as 00:00 h
- If only the month and year are specified and the month and year of first dosing is the same as the month and year of the start date, then use the date of first dosing. If this results in an imputed start date that is after the specified end date, then use the 1st of the month. If the imputed date is the date of first dosing then time will be imputed with the time of first dosing (ie event will be regarded as treatment-emergent)
- If only the year is specified, and the year of dosing is not the same as the year of the start date then use January 01 of the year of the start date. If time is missing this will be imputed as 00:00 h
- If only the year is specified, and the year of dosing is the same as the year of the start date, then use the date of first dosing in the given year. If this results in an imputed start date that is after the specified end date, then use January 01 of the year of start date. If the imputed date is the date of first dosing then time will be imputed with the time of first dosing (ie event will be regarded as treatment-emergent)
- If the start date is completely unknown, then use the date of first dosing. If this results in an imputed start date that is after the specified end date, then use January 01 of the year of the end date. If the imputed date is the date of first dosing then time will be imputed as the start time of first dosing (ie event will be regarded as treatment-emergent)

The following rules will be applied for partial stop dates:

- If only the month and year are specified, then use the last day of the month
- If only the year is specified, then use December 31 of the known year
- If the stop date is completely unknown, do not impute the stop date

Missing or partially missing date and/or times will be imputed as described in [Table 4–1](#) for the calculation of duration of each AE. Adverse event duration is computed in and reported in day and time format: xx d hh:mm.

**Table 4–1: Calculation rules for duration of adverse events**

Data availability	Onset date/time	Outcome date/time	Calculation rules
Complete data	D1/T1	D2/T2	Duration = [(D2 – D1)*24 + (T2 – T1)]/24 d

**Table 4–1: Calculation rules for duration of adverse events**

Data availability	Onset date/time	Outcome date/time	Calculation rules
End time missing	D1/T1	D2/--	End time is substituted by time 23:59h (=23.98 in decimal format) Duration = $\langle [(D2 - D1) * 24 + (23.98 - T1)] / 24 \text{ d}$
Start time missing	D1/--	D2/T2	Onset time is substituted by time 00:00h. Duration = $\langle [(D2 - D1) * 24 + T2] / 24 \text{ d}$
Start and end time missing	D1/--	D2/--	Duration = $\langle D2 - D1 + 1$
Start day and time missing	--/--	D2/T2	Duration = $\langle [(D2 - D0) * 24 + (T2 - T0)] / 24 \text{ d}$ For a subject in the SS, D0 and T0 are the date and time of first administration of PS0018 study medication and for PS0018 screen failures, duration will not be calculated.
End day and time missing	D1/T1	--/--	If the stop date is missing, duration will not be calculated.
Start and end date missing	--/--	--/--	If the stop date is missing, duration will not be calculated.

IMP=investigational medicinal product; SS=Safety Set.

### 4.3 Handling of repeated and unscheduled measurements

All repeated and unscheduled measurements will be presented in the listings, where applicable. The following general rules will apply to all repeated and unscheduled measurements:

- For repeated or unscheduled measurements obtained prior to the first dose of study medication, the latest value (which may be scheduled or unscheduled) prior to the first dose will be used in the calculation of descriptive statistics at each visit;
- For repeated or unscheduled measurements obtained at the designated Baseline visit, the latest value (which may be scheduled or unscheduled) will be defined as the Baseline provided that this occurred prior to the first dose of study medication;
- For repeated or unscheduled measurements obtained at any timepoint after the first dose of study medication, the first value will be used in the calculation of changes from Baseline and for the descriptive statistics (ie in summaries by timepoint). Unscheduled and repeated measurements will not be included in the summaries by timepoint, for all timepoints after the first dose of study medication.

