### **8.12 Unscheduled Visit**

At the Investigator's discretion, an Unscheduled Visit may be completed at any time during the study, but prior to the SFU Visit, if deemed necessary for the subject's safety and well-being.

If an additional visit (or unscheduled visit) is conducted due to safety or efficacy reasons, a C-SSRS assessment will be performed with the subject during the visit. If an additional visit (or unscheduled visit) is conducted for reasons other than safety or efficacy concerns (eg, replacement of lost medication, repeated collection of a laboratory specimen due to collection or analysis issues), a C-SSRS will not be required at these visits.

At this visit, any of the following assessments may be performed, depending on the reason for the visit:

- Vital signs
- Physical examination
- Record 12-lead ECG
- C-SSRS
- If medically indicated, obtain blood sample(s) for:
  - Standard safety laboratory tests (hematology and biochemistry)
  - The blood sample may also be used for PK assessments, if needed

- Obtain urine sample for standard safety laboratory tests (urinalysis; including urine pregnancy test)
- Concomitant medications
- Record AEs

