**Table 9-3: Required investigations and follow-up for PDILI**

Laboratory value		Symptoms a of hepatitis or hypersensitivity	Immediate		Follow up	
ALT or AST	Total bilirubin		Consultation requirements	Actions	Testing	Evaluation
≥3xULN (and ≥2x baseline) and <5xULN (and ≥2x baseline)	<2xULN	No	Discussion with Medical Monitor required. Consider need for hepatology consult if there is no evidence of resolution (see Follow up requirements). c	Further investigation – immediate IMP discontinuation not required (see Section 9.7.1.2 ). IMP discontinuation required if any of the following occur: 
 
• Subject cannot comply with monitoring schedule.
 
• Liver chemistry values continue to increase.
 
• Liver chemistry values remain ≥3xULN (and ≥2x baseline) after 2 weeks of monitoring without evidence of resolution.
 
	Essential: Every attempt must be made to have repeat liver chemistry values and additional testing completed within 48 hours at the site with HCP (see Section 9.7.1.3 ).	Monitoring of liver chemistry values at least twice per week for 2 weeks. d 
 
• Immediate IMP discontinuation required if liver chemistry values continue to increase.
 
 After 2 weeks of monitoring liver chemistry values: 
 
• Discontinue IMP if levels remain ≥3xULN (and ≥2x baseline) without evidence of resolutiond
 
• Continue to monitor until values normalize, stabilize, or return to within baseline values.d
 

ALT=alanine aminotransferase; ASAP=as soon as possible; AST=aspartate aminotransferase; HCP=healthcare practitioner; IMP=investigational medicinal product; NA=not applicable; PDILI=potential drug-induced liver injury; ULN=upper limit of normal

a Hepatitis symptoms include fatigue, nausea, vomiting, and right upper quadrant pain or tenderness; hypersensitivity symptoms include eosinophilia (>5%), rash, and fever (without clear alternative cause).

b If the subject also has ≥2xULN alkaline phosphatase, the possibility of an indication of biliary obstruction should be discussed with the Medical Monitor.

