### 11.3 Clinical laboratory evaluations

Laboratory data (clinical chemistry, hematology, and urinalysis) and changes from Baseline (if applicable) for numeric variables will be listed by PS0016 randomized treatment group and visit. Any laboratory variables with values that are BLQ or ALQ will be handled as described in [Section 4.2.2](#) for calculation of changes from Baseline and for summary tables. Values outside the reference range for the numeric variables will be flagged in the listings.

Clinical chemistry and hematology variables will be summarized by PS0016 randomized treatment group at each visit, for both absolute values and changes from PS0016 Baseline.

Laboratory variables will be grouped according to the laboratory function panel and categorized as normal, high or low, if applicable, based on the reference range supplied by the analytical laboratory. For selected variables that are identified in [Table 11-1](#), the change in category from Baseline will be presented in shift tables at all PS0018 visits.

The number and percentage of subjects with treatment-emergent markedly abnormal (TEMA) laboratory results will be tabulated by PS0016 randomized treatment group and visit. Markedly abnormal laboratory values will be defined as those categorized as Grade 3 and above based on the ranges defined as per the Common Terminology Criteria for Adverse Events (CTCAE) Version 4.03 (2016). These are provided in [Table 14-2](#). The tabulation will include a category for the incidence of TEMA results over all visits which will also count unscheduled measurements.

Laboratory measurements meeting the criteria for TEMA will be listed separately for hematology and chemistry. The listings will include all measurements for any variable with at least one TEMA result for each subject.

Any additional laboratory variables not included in the outputs described previously will be listed separately. These will include the following:

- Pregnancy tests (serum and urine)
- Follicle stimulating hormone (FSH) (only for postmenopausal women)

Subjects with treatment-emergent liver function test abnormalities at any PS0018 visit will be summarized (number and percentage of subjects) by PS0016 randomized treatment group. The criteria for this tabulation are presented in [Table 14-3](#).

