#### **11.4.3 12-Lead Electrocardiograms**

Standard 12-lead ECG will be recorded after 10 minutes of rest in the supine or semi recumbent position. The following ECG variables will be recorded together with the Investigator's interpretation of the ECG profile:

- Heart rate
- PR interval
- QRS duration
- QT interval
- QT corrected for heart rate using Fridericia's formula (QTcF)

The results of all ECG variables will be reported in the by-subject listings. The listing will also include the change from Baseline for numeric parameters and will be presented by PS0016 randomized treatment group and visit.

Measured values and changes from Baseline will be summarized for each variable by PS0016 randomized treatment group and visit.

The following cut-points in QTcF (raw data and change from Baseline) will be summarized categorically by PS0016 randomized treatment group (number and percentage of subjects) and visit. The denominator for the percentages will be the number of subjects with a non-missing measurement for the variable at the specific visit.

Raw QTcF data:

- <450msec
- ≥450 msec to <480msec
- ≥480msec to <500msec
- ≥500msec

Change from Baseline QTcF:

- <30msec
- $\geq 30$ msec to <60msec
- $\geq 60$ msec

Electrocardiogram findings will be listed separately.

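### The QTcF cut-point table is by visit only, so a threshold value first seen at an unscheduled or repeat ECG is listed but counted in no QTcF table

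*SAP*

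**What the plan says.** SAP 4.3 sets the general rule. Every extra measurement goes to the listings: "All repeated and unscheduled measurements will be presented in the listings, where applicable". After the first dose it goes no further: "Unscheduled and repeated measurements will not be included in the summaries by timepoint, for all timepoints after the first dose of study medication". Where a post-dose measurement is repeated, the same section takes the first value for the change from Baseline and the descriptive statistics.

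SAP 11.4.3 plans two ECG tabulations. One gives descriptive statistics by PS0016 group and visit. The other sorts QTcF into bands (the highest is 500 msec or more) and change in QTcF into bands (the highest is 60 msec or more). These bands "will be summarized categorically by PS0016 randomized treatment group (number and percentage of subjects) and visit". On the percentages: "The denominator for the percentages will be the number of subjects with a non-missing measurement for the variable at the specific visit". No exception to SAP 4.3 is stated for ECGs.

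For markedly abnormal (TEMA) laboratory values, SAP 11.3 adds what the ECG section lacks: "The tabulation will include a category for the incidence of TEMA results over all visits which will also count unscheduled measurements".

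Off-schedule ECGs are foreseen. Under Protocol 8.12, "an Unscheduled Visit may be completed at any time during the study", provided it is before the SFU Visit, and a 12-lead ECG is among the assessments that may be done.

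**The concern.** A cut-point table is read for one thing: whether any subject crossed the line. Once the table is confined to scheduled visits and has no whole-study row, it cannot answer that for ECGs taken at other times. Some of those ECGs will have been prompted by a safety question. The QTcF table could show an empty top category while the database holds a qualifying value.

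This matters because the primary objective is long-term safety and change in 12-lead ECG is a named safety variable (Protocol 4.1.2). The SAP also treats the same problem differently from one safety domain to another and gives no reason.

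**Working it through.** There is no stated figure to reproduce. The check follows an ECG value through the rules and then counts how much of the study the table covers.

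**1. Unscheduled ECG.** Take a QTcF of 500 msec or more at an unscheduled visit between Weeks 24 and 48, with scheduled ECGs below the threshold.
- SAP 4.3 sends it to the listing and bars it from summaries by timepoint.
- Both tabulations in SAP 11.4.3 are summaries by timepoint, and neither has an overall or worst-value row.
- Result: it is counted in no QTcF category. The same holds for a change of 60 msec or more.
- SAP 4.3 does not say which study's first dose it means. ECGs taken after the first PS0018 dose fall under the rule on either reading.

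**2. Repeat ECG.** The first value stands. A scheduled value below 500 msec followed by a repeat at or above it stays in the lower band. A scheduled value at or above 500 msec stays counted even if the repeat is lower. Only the first of these cases is lost.

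**3. Scheduled coverage** (Protocol Table 5-1, for a completer).
- ECGs after the first dose: Week 24, Week 48, SFU = 3.
- The last dose is at Week 44, so SFU falls at Week 44 + 20 = Week 64.
- Gaps: 24 − 0 = 24 weeks, 48 − 24 = 24 weeks, 64 − 48 = 16 weeks.
- Time at risk (SAP 11.1.2): 44 × 7 = 308 days from first to last dose, plus 140 = 448 days.

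**4. The four threshold tables side by side.**

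| Table | Whole-study row or count | Unscheduled values |
|---|---|---|
| Laboratory TEMA (SAP 11.3) | Yes | Expressly counted |
| Vital signs TEMA/PCS (SAP 11.4.1) | Yes | Not mentioned |
| Liver abnormalities (SAP 11.3, Table 14-3) | Yes, any PS0018 visit | Not mentioned |
| QTcF cut-points (SAP 11.4.3) | No | Excluded through SAP 4.3 |

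Only QTcF combines a by-visit structure with no whole-study count.

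**5. Early-withdrawal ECG.** These follow SAP 4.4, not 4.3, and two parts of that section pull apart. One bullet leaves an assessment listed only if the visit it maps to does not include that assessment. The closing paragraph maps each domain only to visits where it was planned. An ECG at early withdrawal may therefore reach the table or not, depending on which part is programmed.

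**6. What one subject weighs in an any-time row.** As an illustration only, assume all 45 anticipated subjects roll over, keep the 2:1 PS0016 allocation and have a post-dose ECG. The groups are 45 × 2/3 = 30 and 45 × 1/3 = 15. One subject is then 1/30 = 3.3% or 1/15 = 6.7% of a group, and more if fewer enroll.

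**The case against.** The strongest reply is that nothing is hidden. All ECG results are listed by subject, ECG findings are listed separately, and with at most 45 subjects the listings can be read in full. An abnormal finding that the investigator reports as an adverse event enters the TEAE tables. Keeping irregular extra samples out of by-visit summaries is sound practice. The QTcF categories already go beyond the descriptive ECG statistics promised in Protocol 14.2.2, QT prolongation is not a special-monitoring topic, and the primary variable does not depend on this table.

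Most of that stands, and it limits the point to a reporting gap. It does not close the gap: a TEAE count depends on the investigator's report and is not a QTcF category, and the SAP itself did not think listings sufficient for laboratory TEMA values.

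A reader might infer more than the documents support:
- **That the liver and vital-sign tables lose unscheduled values too.** Protocol Table 9-3 does generate off-schedule liver samples ("Monitoring of liver chemistry values at least twice per week for 2 weeks"). But the liver table and the vital-sign overall row are not summaries by timepoint, so the SAP 4.3 exclusion does not clearly reach them. Liver events have further cover: the laboratory TEMA table counts unscheduled ALT, AST and bilirubin values at its own thresholds, Protocol 9.7.1 requires every PDILI event to be reported as an AE, and SAP 14.3.8 summarizes Hy's Law cases separately. The wording there is only ambiguous.
- **That the error can be stated as a pooled rate among 45 subjects.** The SAP's table of treatment groups for the outputs gives ECG data no All Subjects column, and the QTcF denominators are visit-specific. No such cell is planned.
- **That every unscheduled visit signals a problem.** Protocol 8.12 also names lost medication and repeat specimen collection as reasons.

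**Conclusion.** The gap is real and narrow. As written, a QTcF of 500 msec or more, or a change of 60 msec or more, whose only occurrence is at an unscheduled or repeat ECG enters no QTcF table. It remains in the listings, and in the TEAE tables if reported as an adverse event.

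The undercount in a category equals the number of subjects whose only qualifying value was off schedule or was a repeat. The documents give no expected number of such ECGs, so that could be zero. The conclusion rests on reading SAP 4.3 as it stands, with no unstated exception for ECGs. It does not call into question the by-visit summaries, which are correct for the visits they describe. The correction is worth making because it uses data already collected, follows the SAP's own laboratory approach and could change a reported safety count.

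**What to change.** Add to SAP 11.4.3 an any-time row in both the QTcF and the QTcF-change tables. Suggested wording:

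*For each PS0016 randomized group, subjects will also be classified once by their worst QTcF, and once by their largest increase in QTcF from PS0016 Baseline, at any time after the first PS0018 dose. Scheduled, unscheduled, repeat and early-withdrawal ECGs all count. Percentages use subjects with at least one ECG after the first PS0018 dose.*

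Add a cross-reference in SAP 4.3 so that the row is a stated exception. Leave the by-visit summaries and their first-value rule unchanged.

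Optionally, add a sentence to SAP 11.4.1 and to the liver paragraph of SAP 11.3 saying that unscheduled values count in the vital-sign overall row and in the liver table. This is a clarification, not a correction.

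The cost is SAP wording, one extra row per QTcF table and a little programming. No new data or study procedures are needed.

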### 4.4 Handling of measurements obtained at the withdrawal visit

Subjects who withdraw from the PS0018 study prematurely will be encouraged to return for the early WD visit and the SFU Visit, the latter at 20 weeks following the final dose of study medication.

The following rules will apply with regard to the inclusion of the results obtained at the early WD visit in the descriptive summaries:

- Any efficacy, PK, immunological and safety measurements conducted at the early WD visit should be included in the summaries for the respective scheduled visit, if the early WD visit occurs at the time of the next scheduled visit (within the tolerance window specified in the protocol). For example, if the early WD visit occurs on Day 28, the results would be summarized together with the Week 4 results.
- If the early WD visit does not correspond to the day of a scheduled visit, all assessments of the early WD visit should be mapped to the nearest scheduled visit, relative to the PS0018 Week 0 visit date, following the last scheduled visit where assessments are available.
- If the date of the early WD visit is equidistant between 2 scheduled visits at which no scheduled assessments were performed, the assessments from the early WD visit will be mapped to the earlier of these visits.
- If an EW visit mapping results in data being mapped to a visit where the specific assessment is not actually collected per the protocol schedule of assessments, these data will not be included in the summary statistics and will be listed only.
- The only exception to the above rule is for ADA (for both BKZ and CZP) assessments, in which all early withdrawal visit assessments will be assigned to the next scheduled visit at which ADA are assessed. The rationale for this is that ADA positivity is summarized over a given study period. As part of that summary, a table indicating the first visit at which ADA positivity is observed will be presented. In order to match the number of subjects who were ADA positive at specific visits with the overall positivity for the period, it is necessary to ensure that ADA positivity is attributed to a visit where ADA antibody assessments were performed.

Assessments from the EW visit will be displayed as the mapped visit and will be flagged in the by-visit data listings.

For example, vital sign assessments are performed at PS0018 Weeks 0, 4, 8, 12, 16, 20, 24, 28, 32, 36, 40 and 44. If a subject discontinues on Day 37, and the previous vital sign assessment was done at Week 4 (Day 28), the nearest scheduled assessment (following the last visit at which assessments were available) would be Week 8 (Day 56). Therefore, the early WD visit assessment should be re-assigned to the Week 8 visit.

However, if a subject discontinues at Day 37, and the previous vital sign assessment was done at PS0018 Week 0, the early WD visit assessments would be re-assigned to the Week 4 (Day 28) visit, which would be the nearest scheduled visit relative to the PS0018 Week 0 visit date.

Different domains (eg vital signs, ECG, safety laboratory tests, PASI, IGA) from the same early WD visit may be re-assigned to different study visits depending on the study schedule of assessments, ie measurements obtained at the early WD visit can only be mapped to a scheduled visit at which the respective assessment was intended to be measured. Assessments from the early WD visit that are mapped to scheduled visits will be flagged in the data listings.

